The inclusion and exclusion criteria for the PRECAR trial are described in Table 1. Briefly, two independent cohorts (cirrhosis cohort and HBV infection cohort) will be recruited for surveillance of HCC. The cirrhosis cohort will be consisted of patients with biopsy diagnosis or distinctive clinical characteristics of cirrhotic liver regardless etiology of cirrhosis. For HBV infection cohort, seropositivity of hepatitis B surface antigen is the basic condition for inclusion.

Overview of trial design

PRECAR is a prospective, observational, multicenter trial surveilling development of HCC in patients with cirrhosis or HBV infection. In PRECAR, the aim will be to recruit a total of 10,000 patients (5000 each for the two cohorts) from a minimum of 10 sites. Follow-up will be carried out for eligible patients for collection of demographic, clinical, and serological characteristics and samples for analyses. For those who developed HCC, hepatic resection will be the standard

of care unless unresectable. Data of interest and schedule for the PRECAR trial are summarized in Table 2.

Outcome measures

The primary endpoints of the PRECAR trial include development of HCC, overall survival (OS), and liver-related disease progression (LDP). Secondary endpoints are development of non-HCC malignant neoplasm, such as intrahepatic cholangiocarcinoma, liver resection rate (LRR), and postoperative overall (POS) and relapse-free survival (PRFS) after development of liver malignant neoplasm.

Outcome definitions

HCC – the time from the date of inclusion to development of HCC.

OS – the time from the date of inclusion to death from any cause.

LDP – the time from the date of inclusion to non-malignancy-associated liver-related disease progression or death, whichever is earlier.

Non-HCC – the time from the date of inclusion to development of non-HCC malignant neoplasm.

LRR – the number of malignancy-developed patients whose tumor is resectable without vascular invasion and extrahepatic metastasis.

POS – the time from the date of liver resection to death from any cause.

PRFS – the time from the date of liver resection to tumor progression in the liver or death, whichever is earlier.

Blood collection for biosignature analysis

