Peripheral blood samples (25 ml) will be collected from all consenting patients at first 3 follow-up (0, 6th, and 12th month), which will be used to develop a biosignature to stratify patients at high risk for development of HCC. After development of a biosignature, 20 ml of peripheral blood samples will be collected from patients at high risk for HCC at 4th to 7th follow-up for modification and validation of the biosignature.

Statistical analysis

All statistical analyses will be performed using R (<http://www.r-project.org/>) or SPSS (Chicago, IL). Cox hazards proportional model and logistic regression will be applied to screen factors for the inclusion in a biosignature. Correlation test will be performed between results of multivariate Cox and logistic regressions, and false-positive factors will be deleted. After screening covariates, receiver operating characteristic (ROC) curves will be constructed to calculate optimum threshold for setting of cut-off value to define high risk for HCC. Independent demographic and clinical prognostic factors may be combined with the biosignature to improve performance sensitivity and specificity. Predictive signatures for cirrhosis cohort and HBV infection cohort will be developed independently. A correction for multiple testing may be applied.

Discussion

The PRECAR trial will identify predictors for development of HCC and diagnosis of very early

HCC by comparing HCC cases arising from cirrhosis or HBV infection with non-HCC developing cases. To the best of our knowledge, no prospective observational cohort trial has been published with intent to develop a biosignature to stratify patients at high risk for HCC. However, a case control study with similar design (miRNA as a diagnostic tool for HCC) is ongoing in South Africa, where HIV is hyper endemic, thus the etiology of HCC is different from the PRECAR.¹⁶ In addition, ideal aim of the PRECAR trial is to successfully stratify patients who have high potential to develop HCC and carry out intensive follow-up to prevent up to 6 months of disease progression, as well as to offer curative therapeutic options at very early stage to improve prognosis.

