Surveillance for HCC has been introduced as an effective strategy to improve prognosis of patients with HCC.¹⁷ However, this field remains to be considered immature due to absence of validation of previous studies and limited accuracy that reduced cost-effectiveness. In recent years, the development of powerful tools, such as genome sequencing, plasma-free DNA sequencing, and high-throughput protein expression screening, suggests that the establishment of a biosignature could improve sensitivity and specificity of current surveillance method. The current surveillance, which is consisted of biannual ultrasonography and α -fetoprotein, reveals limited accuracy, false-positivity, and not efficient in a timely manner. Especially, these are confined to detect already-developed HCC, indicating that if HCC occurred a month after routine surveillance, the tumor will progress for 5 followed months before the next surveillance. Regarding aggressive characteristics and rapid progression, advancement of the tumor is likely to derive patient a worse candidate for curative treatments and deteriorates survival outcomes.

The biosignature developed from PRECAR trial will improve predictive and diagnostic

accuracy for HCC in settings with cirrhosis and HBV infection. During the establishment of the PRECAR biosignature, developmental process of HCC will be further elucidated and translated to improve predictive and diagnostic accuracy. We believe that the PRECAR biosignature will be useful in stratifying patients with cirrhosis or HBV infection at high risk for HCC, as well as in diagnosing HCCs at very early stage.

Trial status

The PRECAR trial is currently ongoing. Patient recruitment will be closed on 15 July 2019 with estimated participant number of 10,000 (5000 for cirrhosis cohort and 5000 for HBV infection cohort). The final analysis will be triggered after 3 years of additional follow-up for enrolled patients for validation of the PRECAR biosignature.

References

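### The HCC risk signature has no stated prediction horizon, censoring handling or rule for the month 0, 6 and 12 samples, so samples drawn at the diagnosis visit can pass as predictive

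*Combined protocol and SAP*

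**What the plan says.** Outcome definitions makes HCC a time-to-event endpoint: "the time from the date of inclusion to development of HCC". Statistical analysis then names two screening models ("Cox hazards proportional model and logistic regression will be applied to screen factors for the inclusion in a biosignature"), a cross-check ("Correlation test will be performed between results of multivariate Cox and logistic regressions, and false-positive factors will be deleted") and a cut-off rule ("receiver operating characteristic (ROC) curves will be constructed to calculate optimum threshold for setting of cut-off value to define high risk for HCC").

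Under Blood collection for biosignature analysis, the first three samples are "collected from all consenting patients at first 3 follow-up (0, 6th, and 12th month), which will be used to develop a biosignature" for stratifying HCC risk. Later samples come "from patients at high risk for HCC at 4th to 7th follow-up for modification and validation of the biosignature". Table 2 marks sample collection at all seven visits without that restriction, and endpoint evaluation at every visit from month 6.

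The Abstract gives one year of recruitment and three years of six-monthly follow-up. Trial status adds: "The final analysis will be triggered after 3 years of additional follow-up for enrolled patients for validation of the PRECAR biosignature". The Discussion states both a predictive and a diagnostic aim: "The PRECAR trial will identify predictors for development of HCC and diagnosis of very early" HCC.

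No section states a prediction horizon for the logistic model or the ROC curve, how patients lost or not yet fully followed are classed, how death before HCC is treated, or which sample is analysed against which later period.

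**The concern.** Logistic regression and an ordinary ROC curve need a yes/no outcome. For a time-to-event endpoint that label means something only at a stated horizon, with a rule for patients not observed that far. Here both are left to the analyst.

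The more serious gap concerns the samples. From month 6, blood is drawn at the same visit at which HCC is looked for. If a sample from the visit of diagnosis counts as a predictor, the marker may be measuring a tumour already present. The risk signature would then borrow diagnostic accuracy and report it as predictive accuracy. At stake are the meaning of high risk, the sensitivity and specificity quoted for it, and who is sampled from visit 4 on if sampling is restricted to high-risk patients.

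**Working it through.** The plan has no figure of its own to reproduce: it gives no HCC incidence, death rate, loss rate or marker effect. The dates and visits come from the documents. The rates are assumptions: constant hazards of HCC 0.03, death 0.03 and loss 0.05 per year, total 0.11.

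**1. Follow-up when the signature is built.** Restricted sampling at visit 4 needs a signature by the first patients' month 18. With 12 months of recruitment, the last patient is then at 18 − 12 = 6 months. If development waits for everyone's month-12 sample, the first patient is at 12 + 12 = 24 months. Follow-up therefore spans about 6–18 or 12–24 months, taken as uniform. The second fits better with using month-12 samples from all patients.

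**2. Cases found at a sampling visit (12–24 month cut).** Suppose HCC is found only at scheduled visits. Each half-year multiplies the number at risk by exp(−0.11 × 0.5) = 0.946. Relative numbers found are 1 at month 6, 0.946 at month 12, and 0.5 × 0.896 = 0.448 at month 18, which only half the patients have reached. The share found at month 6 or 12 is 1.946 / 2.394 = 81%.

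**3. Effect on apparent AUC.** Take a normal marker with HR 1.3 per SD. The mean difference between cases and non-cases is about ln 1.3 = 0.262 SD, and AUC = Φ(difference / √2).

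- No tumour effect: Φ(0.262/1.414) = 0.57 (one simulation put it at 0.58).
- Shift of 0.5 SD at the diagnosis visit: Φ(0.762/1.414) = 0.705 in affected cases. Overall 0.81 × 0.705 + 0.19 × 0.574 = 0.68.
- Shift of 1 SD: Φ(1.262/1.414) = 0.814. Overall 0.81 × 0.814 + 0.19 × 0.574 = 0.77.
- If only 40% of cases were affected: 0.4 × 0.705 + 0.6 × 0.574 = 0.63, or 0.4 × 0.814 + 0.6 × 0.574 = 0.67.
- If only month-0 samples were used, this mechanism would add nothing.

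**4. Effect of unequal follow-up on 12-month risk.** With death as a competing event, true risk is (0.03/0.06)(1 − e^(−0.06)) = 2.9%. Observed HCC by time t is F(t) = (0.03/0.11)(1 − e^(−0.11t)), so F(1) = 2.84%. The mean of F over 6–12 months is 2.16%.

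- 6–18 month cut, incomplete patients coded as non-cases: 0.5 × 2.84 + 0.5 × 2.16 = 2.5%.
- Same cut, incomplete patients excluded: HCC-free at 12 months is 0.5 × e^(−0.11) = 44.8%, and observed deaths before HCC are 2.5%. Risk is 2.5 / (2.5 + 44.8 + 2.5) = 5.0%.
- 12–24 month cut: coded as non-cases 2.8%; excluded 2.84 / (2.84 + 89.6 + 2.84) = 3.0%.

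**5. Effect on association and discrimination.** In simulations with these HCC and death rates and a marker HR of 2 per SD, AUC was 0.69 at either cut against 0.69–0.70 at 36 months. Loss of 2–10% per year unrelated to the marker moved the 36-month OR by at most 0.02 and AUC by at most 0.002. If loss at 5% per year also had HR 2 per SD, a true OR of 1.98 became 1.83 (lost coded as non-cases) or 2.08 (lost excluded).

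**The case against.** The case on the other side is substantial, and much of it stands.

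- The documents do not show that a wrong analysis is planned. Cox handles censoring, the endpoint has a time origin, the logistic outcome is not named, and a time-dependent ROC is not ruled out. A reader might infer that a naive yes/no analysis is intended. The text does not say so; this is a gap in specification. Logistic regression is also legitimate for the diagnostic aim.
- A reader might infer that the early samples have no tie to later HCC at all. That goes too far: their stated purpose is to develop the risk signature. What is missing is the analytic rule.
- The month-0 sample is largely pre-HCC already. Table 1 excludes diagnosed malignancy, and Table 2 has no endpoint evaluation at month 0. The ambiguity concerns months 6 and 12.
- Modification and validation at visits 4–7, and the final analysis, can correct an early cut-off. The Cox/logistic comparison, read factor by factor, can remove false factors. Both are partial safeguards: if later sampling is restricted, new samples come only from patients already labelled high risk, and the cross-check does not cover the cut-off or the choice of sample.
- It might be said that 36 months is the implied horizon. The documents give it as study duration and the timing of validation, and it cannot serve a cut-off needed near month 18.
- Unequal follow-up does little harm at the later cut or to AUC. That is correct, so the point should not be argued as a badly biased cut-off.

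**Conclusion.** The point holds as an under-specified risk analysis that is cheap to improve. As written, nothing keeps samples from the visit of diagnosis out of the risk signature, and nothing fixes the horizon or the treatment of incomplete follow-up.

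The larger effect is the same-visit one: apparent AUC of 0.68–0.77 in place of about 0.57. It rests on HCC being found only at scheduled visits, on a marker HR of 1.3 per SD, on an assumed tumour-driven shift of 0.5–1 SD, and on those samples being used as predictors. The follow-up effect is confined mainly to absolute risk at an early cut and is negligible at 12–24 months. OR and AUC barely move if the marker effect is constant and loss is unrelated to the marker. All rates are assumptions, so the figures show possible size and are not forecasts for this cohort.

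**What to change.** In Statistical analysis, for risk prediction, state that:

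- only samples taken before the visit at which HCC is found are used, in patients HCC-free at that sample. Month 0 is the main landmark, with months 6 and 12 added when events allow. Samples from the diagnosis visit go to the diagnostic analysis;
- Cox regression is the primary risk screen;
- the cut-off, sensitivity and specificity come from a time-dependent ROC with inverse-probability-of-censoring weights at a named horizon that the data support, for example 12 months after the landmark at development. They are re-estimated at 36 months from inclusion in the final analysis, with death before HCC as a competing event;
- logistic regression is kept for diagnosing current HCC, or for risk only at that horizon with censoring weights.

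The cost is plan wording and modest extra analysis in R, which the plan already names; no new visits or data are needed. The drawback is fewer events at later landmarks. Under the assumed rates, HCC cases per 5000 after month 12 number 5000 × 0.5 × the mean of [F(t) − F(1)] over 12–18 months, about 16–17, at the 6–18 month cut. They number about 65 at the 12–24 month cut and 5000 × [F(3) − F(1)] = 241 at month 36. The month-12 landmark is therefore thin until the final analysis.

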| Physical and clinical assessment | | | | | | | |
| Height | x | | | | | | |
| Weight | x | x | x | x | x | x | x |
| Blood pressure | x | x | x | x | x | x | x |
| Body temperature | x | x | x | x | x | x | x |
| Routine blood test | x | x | x | x | x | x | x |
| Liver function test | x | x | x | x | x | x | x |
| Renal function test | x | op | op | op | op | op | op |
| Electrolyte test | x | op | op | op | op | op | op |
| Blood glucose | x | | | | | | |
| Glycosylated hemoglobin | x | | | | | | |
| Blood lipid | x | | | | | | |
| Hepatitis virus | x | | | | | | |
| HBV DNA ^a | x | x | x | x | x | x | x |
| HIV antibody | x | | | | | | |
| Serum tumor markers | x | x | x | x | x | x | x |
| Ascites ^b | op | op | op | op | op | op | op |
| INR | x | x | x | x | x | x | x |
| Ultrasonography | x | x | x | x | x | x | x |
| Contrast enhanced CT or MRI ^c | x | op | op | op | op | op | op |
| Liver hardness | x | x | x | x | x | x | x |
| Child-Pugh score | x | x | x | x | x | x | x |
| Endpoints evaluation | | x | x | x | x | x | x |
| Sample collection | x | x | x | x | x | x | x |

HBV, hepatitis B virus; HIV, human immunodeficiency virus; INR, international normalized ratio; CT, computed tomography; MRI, magnetic resonance imaging.

^arequired for patients with HBV infection.

^brequired for patients with ultrasonography results indicating ascites.

^crequired for patients with ultrasonography results indicating hepatic nodules.

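### The only firm false-positive step is a Cox–logistic comparison with no stated rule, and the plan specifies neither an optimism correction nor a validation method for the cut-off

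*Combined protocol and SAP*

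**What the plan says.** **Selection (Statistical analysis).** Cox and logistic regression both screen candidate factors. Then: "Correlation test will be performed between results of multivariate Cox and logistic regressions, and false-positive factors will be deleted". The outcome of each model, the statistic compared and the deletion rule are not stated. On multiplicity the section says only: "A correction for multiple testing may be applied".

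**Cut-off (same section).** After screening, "receiver operating characteristic (ROC) curves will be constructed to calculate optimum threshold for setting of cut-off value to define high risk for HCC". No split sample, bootstrap, cross-validation or shrinkage is described anywhere. Signatures are built separately in each cohort of 5000.

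**Samples (Blood collection for biosignature analysis).** For development: "Peripheral blood samples (25 ml) will be collected from all consenting patients at first 3 follow-up (0, 6th, and 12th month". Later samples are "collected from patients at high risk for HCC at 4th to 7th follow-up for modification and validation of the biosignature".

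**Validation (Trial status).** "The final analysis will be triggered after 3 years of additional follow-up for enrolled patients for validation of the PRECAR biosignature". No metric, locked version or method follows.

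**Schedule (Table 2).** Endpoint assessment is marked at every visit after baseline, to month 36, with no limit by risk group: "Endpoints evaluation | | x | x | x | x | x | x". Sample collection is marked at all seven visits, also without a limit, which does not match the blood collection section.

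**The concern.** The candidates come from genome sequencing, plasma-free DNA sequencing and high-throughput protein screening, where chance findings are a leading risk. Agreement between two models protects against them only if the models bring independent information. Two regressions of the same outcome on the same markers in the same patients do not.

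The trial's product is a cut-off with a claimed sensitivity and specificity. If selection, weighting and threshold all come from one data set, the apparent figures are too good. A check confined to patients already labelled high risk contains no test-negatives, so it cannot reveal missed cases. If the same samples also modify the signature, they do not validate the modified version. What is at stake is the reported accuracy and its later use. Table 2 does not vary the scheduled assessments by risk group.

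**Working it through.** The documents give no marker count, alpha, HCC rate, event count or effect size, so there is no stated figure to reproduce. All of these are assumed below.

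**1. Does agreement remove chance findings?**

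From the documents: 5000 patients per cohort and follow-up to 36 months. Assumed: pure-noise independent markers with one baseline value each, 3-year HCC incidence 1–20%, attrition 5.5–20% per year, two-sided alpha 0.05, and deletion unless significant in both models with the same sign.

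- One model on 1000 noise markers: 1000 × 0.05 = 50 chance findings expected.
- Two independent tests would leave 1000 × 0.05² = 2.5.
- Same patients and HCC events to month 12: the z-values correlate at 0.997–1.000, and 92–100% of Cox chance findings survive (43–52 per 1000).
- Events to month 36: 74–98% survive (38–49 per 1000). A second set of runs gave 81–98%.
- Multivariable fits, 44–351 events: 86–100% survive. About 1 of 20, 1.4–2.3 of 40 and 4–7 of 100 noise candidates remain. With no filter, alpha alone predicts 1, 2 and 5.
- Logistic outcome changed to death: only 3–6% survive.

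A formula explains the pattern. For correlation r, the two z-values differ with SD √(2(1−r)). The share of chance findings lost is about 2 × φ(1.96) × 0.399 × SD / 0.05, with φ(1.96) = 0.0584.

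- r = 0.997: SD 0.077, loss about 0.07, so 93% survive.
- r = 0.995: SD 0.10, loss about 0.09, so 91% survive.
- Survival of 81% or 74% needs r of about 0.98 or 0.96. The correlation range 0.995–1.000 therefore describes month-12 events, or up to 3 years with at most 7% annual loss. It does not describe the 36-month settings with the heaviest attrition.

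**2. How optimistic is the cut-off?**

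Assumed: 10 real markers among 20, 40 or 100 candidates, attrition 10% per year (HR 1.3 rows), the same filter, a Cox refit, and a Youden cut-off on events to month 12. Youden index = sensitivity + specificity − 1. Optimism is apparent minus fresh patients at month 12. The remainder is fresh minus later HCC (months 12–36, all still followed).

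| HR per SD | Events | Candidates | Apparent | Fresh | Later | Optimism | Remainder |
|---|---|---|---|---|---|---|---|
| 1.3 | ~49 | 20 | 0.40 | 0.20 | 0.19 | 0.20 | 0.01 |
| 1.3 | ~49 | 40 | 0.40 | 0.17 | 0.18 | 0.23 | −0.01 |
| 1.3 | ~49 | 100 | 0.49 | 0.16 | 0.13 | 0.33 | 0.03 |
| 1.3 | ~169 | 20 | 0.36 | 0.29 | 0.29 | 0.07 | 0.00 |
| 1.3 | ~169 | 100 | 0.39 | 0.28 | 0.28 | 0.11 | 0.00 |
| 1.3 | ~362 | 20 | 0.35 | 0.32 | 0.31 | 0.03 | 0.01 |
| 1.3 | ~362 | 100 | 0.36 | 0.30 | 0.29 | 0.06 | 0.01 |
| 1.6 | ~52 | 20 | 0.59 | 0.47 | 0.45 | 0.12 | 0.02 |
| 1.6 | ~52 | 100 | 0.64 | 0.45 | 0.43 | 0.19 | 0.02 |
| 1.6 | ~187 | 20 | 0.55 | 0.53 | 0.47 | 0.02 | 0.06 |
| 1.6 | ~187 | 100 | 0.56 | 0.50 | 0.48 | 0.06 | 0.02 |
| 2.0 | ~222 | 20 | 0.69 | 0.68 | 0.61 | 0.01 | 0.07 |
| 2.0 | ~222 | 100 | 0.70 | 0.67 | 0.58 | 0.03 | 0.09 |
| 2.0 | ~507 | 20 | 0.68 | 0.66 | 0.54 | 0.02 | 0.12 |
| 2.0 | ~507 | 100 | 0.68 | 0.66 | 0.55 | 0.02 | 0.11 |

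The remainder reflects depletion: high-scoring patients develop HCC earlier and leave the risk set. Resampling estimates the fresh-patient value, so it corrects optimism but not depletion. At HR 1.3, five-fold cross-validation of the whole process came within 0.03 of the fresh-patient value in all nine settings.

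**3. Can high-risk patients alone validate the cut-off?**

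No. Sensitivity needs the HCC cases labelled low risk, and specificity needs the non-cases labelled low risk. Under a Youden cut-off, 40–59% of later HCC fell in patients labelled low risk at HR 1.3, and 24–39% at HR 1.6–2.0. With the cut-off set at 90% apparent sensitivity, the share was about 12–31%.

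**The case against.** **The filter tested is one reading.** The plan gives no rule, and significant-in-both is assumed here. The Abstract feeds both HCC and overall survival into the biosignature, so the two models might have different outcomes, and the step would then behave quite differently. This stands as a condition. The same-outcome reading is still the more likely one: no separate data are named, blood comes from all consenting patients, and the Discussion describes "comparing HCC cases arising from cirrhosis or HBV infection with non-HCC developing cases". On either reading the rule is missing.

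**A reader might infer that reported accuracy must collapse.** The documents do not support that. The large fall needs weak markers and few events, and its worst row fits 100 candidates on about 49 events (0.49 events per candidate), which many analysts would not attempt. The marker effect and the Youden rule are assumptions; the plan says only that the threshold is optimal, and the Introduction stresses sensitivity.

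**A reader might infer that no all-patient validation is planned or possible.** That also goes too far. Trial status refers to enrolled patients without a high-risk limit, and the blood collection section restricts samples, not outcomes. What is missing is the method, the metric and a locked version.

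**A better selection method may gain little.** At HR 1.3, from about 169 events, the filter, false discovery rate (FDR) control and a lasso Cox model differed by at most 0.015 in later AUC. This stands: the main gain is honest performance figures, not a better signature.

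**Conclusion.** The point holds in conditional form. If both models use the same patients and HCC outcome, Cox–logistic agreement is not false-positive control: roughly 74–100% of chance findings survive under the assumed rule. That range rests on independent markers measured once, whereas the plan samples at months 0, 6 and 12.

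The cut-off has no described optimism correction, and the high-risk visit 4–7 samples cannot by themselves give its sensitivity or specificity. Both statements follow from the text and need no simulation.

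The size of the optimism is not settled by the documents. It is large with weak markers and about 50 events, and mostly about 0.02–0.1 on the Youden scale with stronger markers or 150 or more events. The exceptions include HR 1.6 at about 52 events (0.12–0.19). Part of any further fall on later HCC is depletion and should not be blamed on missing resampling. This should be fixed; confidence is high in the gap in the plan and lower in any single magnitude.

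**What to change.** 1. Do not treat Cox–logistic agreement as false-positive control. Pre-specify one time-to-HCC selection method per cohort, preferably a penalised Cox model. If different patients or endpoints were intended, state them and the deletion rule. FDR control is not an equal substitute when events are few: at about 49 events (HR 1.3) it kept 1.1–2.4 of 10 real markers against 4.5–4.8 for the filter, with later AUC 0.55–0.60 against 0.61–0.65 (lasso Cox 0.61–0.66).
2. Repeat screening, selection, weighting and cut-off choice inside bootstrap or cross-validation. Report optimism-corrected AUC, sensitivity, specificity and calibration.
3. Lock the signature and cut-off from month 0–12 samples and evaluate them, unmodified, against later HCC in all followed patients, low-risk included. Report this separately from the resampling estimate, because depletion affects only the former. The Discussion mentions intensive follow-up of high-risk patients; state whether it occurs within the trial, since it would bias HCC ascertainment by label.
4. Report any version modified with visit 4–7 samples as not validated.
5. Reconcile the blood collection section, Trial status and Table 2 on who gives samples at visits 4–7 and who is in the validation.

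**Cost.** SAP wording and computing time. Endpoint evaluation is already scheduled to month 36, so no visits or samples are added. Reported accuracy will probably be lower. Validated sensitivity will be imprecise if later cases are few: at sensitivity 0.5, 1.96 × √(0.25/n) gives ±11 points at 80 later cases, ±6 at 260 and ±4 at 500.

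### Marker screening ignores enrolling site, so differences between sites can let null markers through, and the Cox-versus-logistic check cannot take them out

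*Combined protocol and SAP*

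**What the plan says.** All references are to the combined protocol and SAP.

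- **Sites.** Overview of trial design: the aim is to "recruit a total of 10,000 patients (5000 each for the two cohorts) from a minimum of 10 sites".
- **Markers.** The Discussion names the tools, "such as genome sequencing, plasma-free DNA sequencing, and high-throughput protein expression screening". The number of candidate markers is not given.
- **Screening.** Statistical analysis: "Cox hazards proportional model and logistic regression will be applied to screen factors for the inclusion in a biosignature". Site does not appear there as a covariate, stratum, random effect or batch term, and the covariates of the multivariate models are not listed.
- **Protection against false positives.** One definite step, "Correlation test will be performed between results of multivariate Cox and logistic regressions, and false-positive factors will be deleted", and one optional step, "A correction for multiple testing may be applied". No alpha is stated.
- **Case mix.** Eligible population: cirrhosis patients may enter on biopsy or on "distinctive clinical characteristics of cirrhotic liver regardless etiology of cirrhosis".
- **Samples.** Blood collection for biosignature analysis gives volumes and visits. It has no rule on processing, shipping, central assay or batching.
- **Validation.** The same section uses later samples from high-risk patients of the same study. No held-out or external site is named.

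**The concern.** Sequencing and protein assays can be sensitive to how blood is handled, and handling may differ between hospitals. HCC risk may differ too, since cirrhosis of any cause is eligible. When both differ, a marker that only identifies the hospital is associated with HCC in the pooled data, even though it says nothing about risk within a hospital.

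Comparing a Cox fit with a logistic fit tests whether the result depends on the choice of model. It does not test confounding, because both fits share the patients, the events and any site imbalance. Developing the two cohorts separately removes cirrhosis-versus-HBV differences but not site differences within a cohort.

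The signature is meant for clinical use. A marker that stands in for the enrolling hospital would carry no information at a new one.

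**Working it through.** The plan states no figure that could be reproduced here, so the check asks when the mechanism operates and how large it could be.

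**Inputs.** From the documents: 5000 patients per cohort and at least 10 sites, so 5000 / 10 = 500 per site if sites are equal. Assumed, because the documents are silent: 10 or 20 equal sites (S), m = 5000 / S patients per site, HCC proportion p of 3% or 8%, between-site SD of HCC log-odds τ of 0.1 to 0.5, marker intraclass correlation ρ of 0.02 to 0.10, two-sided 5% tests. For scale, an SD of 0.3 in log hazard means an expected ratio of about 2.5 between the highest- and lowest-risk of 10 sites; 0.5 means about 4.7.

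**Step 1: approximate formula.** For a marker with no within-site link to HCC, ignoring site inflates the variance of the score statistic to about

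φ = 1 + m × ρ × τ² × p(1 − p) × (S − 1)/S,

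and the false-positive rate is 2[1 − Φ(1.96/√φ)]. Because ρ and τ² multiply, there is no inflation if either is zero.

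- Top of the range (S = 10, p = 0.08, τ = 0.5, ρ = 0.10): φ = 1 + 500 × 0.10 × 0.25 × 0.0736 × 0.9 = 1.828; 1.96/√1.828 = 1.450; rate 14.7%.
- Bottom of the range (S = 20, p = 0.03, τ = 0.1, ρ = 0.02): φ = 1 + 250 × 0.02 × 0.01 × 0.0291 × 0.95 = 1.0014; rate 5.0%.

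Rates from the formula as ρ goes from 0.02 to 0.10:

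| τ | 10 sites, 8% HCC | 10 sites, 3% HCC | 20 sites, 8% HCC | 20 sites, 3% HCC |
|---|---|---|---|---|
| 0.1 | 5.1–5.4% | 5.0–5.2% | 5.0–5.2% | 5.0–5.1% |
| 0.3 | 5.7–8.5% | 5.3–6.4% | 5.4–6.8% | 5.1–5.7% |
| 0.5 | 6.9–14.7% | 5.8–8.9% | 6.0–10.2% | 5.4–7.0% |

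**Step 2: simulation of the same settings.** With 10 sites and 8% HCC, two independent sets of null-marker score tests gave 6.1%, 7.4%, 9.3% and 5.7%, 6.6%, 8.6% at τ = 0.3 (ρ = 0.02, 0.05, 0.10), and 6.6%, 9.8%, 14.1% and 7.1%, 10.3%, 15.1% at τ = 0.5. Stratified by site, the rates were 4.7% to 5.4%. The formula and the simulations agree.

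**Step 3: does the Cox-versus-logistic check help?** A separate simulation fitted both models (5000 patients, 10 equal sites, 3 years, 15% censored early, 3-year HCC risk 3% or 9%, 2400 null markers per scenario).

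- If only marker level or only HCC risk differed by site, or neither did, the rate was 4.2% to 5.6%.
- Cox and logistic z statistics correlated at 0.997 to 0.9995 throughout.
- When both marker level and HCC risk differed by site, 94% to 99% of logistic false positives were also significant in Cox. The check removes almost none of them.
- Stratifying by site gave 4.6% to 5.8% (logistic) and 4.5% to 5.6% (Cox).

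The most extreme scenario there (9% HCC, hazard SD 0.5, marker between-site SD 0.5 of the within-site SD, so ρ = 0.25/1.25 = 0.20) reached 23.8%. Its ρ and HCC rate lie outside the range above, so it is a stress case only.

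**Step 4: counts.** Per 1,000 null candidates, 5% is 50 false positives and 14% to 15% is 140 to 150. Site stratification removes at most the excess of about 90 to 100; the 50 remain.

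**The case against.** **No between-site data.** A reader might infer that site differences do produce false-positive markers in this trial, or that its signature will fail at other hospitals. The documents support neither. They give no site-level HCC rates or marker variation. They are silent on sample processing, which does not show that samples were processed locally or exclude a central laboratory. This stands: the claim can only be that null markers can be selected.

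**Size.** A reader might take 6% as a floor and 14% as typical. Neither follows. At τ = 0.1 the rate cannot be told from 5%. The plan says at least 10 sites, and with equal sites more sites means less inflation, though unequal sizes could raise it again. The signature is first developed on samples from months 0, 6 and 12, before sampling of high-risk patients from month 18. The first screen may therefore rest on fewer events than full follow-up would give, which points to the lower HCC columns. All of this stands.

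**Covariates.** The multivariate models might include etiology or liver function and absorb some case mix. That is possible, but the covariates are not listed, and clinical factors would not remove handling effects.

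**Multiplicity matters more.** In much of the range this is right. With a Bonferroni threshold for 1,000 markers, the unstratified screen in step 3 left about 0 to 3 false markers per 1,000 where both marker level and risk differed by site, except about 20 in the stress case. But the plan says only that a correction may be applied.

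None of these objections rescues the Cox-versus-logistic comparison as a guard against site confounding.

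**Conclusion.** The point holds in conditional form. The plan screens markers across at least 10 sites without using site, and its one definite false-positive check cannot detect site confounding. Inflation requires marker level and HCC risk both to vary between sites. Under the assumed values, the rate at a nominal 5% lies between about 5% and about 14% to 15%, and near 5% when stratified by site. Confidence in any particular size is low, because every input except the cohort size and the minimum number of sites is an assumption, and the calculations are univariable with equal-sized sites. This is a worthwhile inexpensive improvement, not evidence that the study's results are invalid.

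**What to change.** Add to Statistical analysis: at the screening step, the Cox model is stratified by enrolling site and the logistic model is conditioned on site; the final signature is then fitted without a site term so that it can be applied elsewhere.

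**Cost.** One or two sentences and a stratification term, with no new patients or visits. It needs enrolling site in the analysis file. Table 2 does not list it, but a multicenter study can be expected to hold it.

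**Downsides.** Very small sites contribute little to the screen, and some between-site information is lost. With 10 equal sites and 3% to 8% HCC there would be 500 × 0.03 = 15 to 500 × 0.08 = 40 events per site per cohort, which a stratified or conditional analysis can use. Because the final fit omits site, between-site differences can still affect the coefficients of retained markers; setting them beside the site-stratified coefficients would show this.

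**What it does not do.** It does not replace multiplicity control. The plan should state the alpha and make a correction mandatory.

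**Separate and optional.** Where assays have not yet been run, each site's cases and controls could be spread across batches. This is a laboratory step with its own cost. The document is dated 30 April 2020 and gives 15 July 2019 as the close of recruitment, so it may be too late for some samples.
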